2.4.5.4 Analyses of vital sign variables

The summary statistics (including number, mean, median, Q1, Q3, standard deviation, minimum and maximum) of all vital sign variables (actual values and changes from baseline) will be calculated for each visit or study assessment (baseline, each postbaseline time point) by treatment group.

Vital signs values will be listed.

2.4.5.5 Analyses of immunogenicity

Immunogenicity assessments on serum samples will be performed at Ablynx GLP using 4 validated methods. The results of the analysis will be transferred to SGS Secure Data Office in Excel format. Results will be reported as log₁₀ (titer).

2.4.5.5.1 Available data

The available parameters per sample are:

- Anti-drug antibody (ADA) log₁₀(titer) (no data imputation). Titers <log₁₀ are considered ADA negative.
- Modified anti-drug antibody (mADA) assay log₁₀(titer) (for subset of subjects only, no data imputation)
- Neutralizing antibody (NAb) log₁₀(titer) (for subset of samples only, data imputation required for ADA negative samples)
- NECA log₁₀(titer) (for subset of samples only, data imputation required for ADA negative samples)

Based on the above listed data per subject, a subject classification will be attributed for each assay, resulting in the following reported data per subject:

- ADA subject classification (all subjects)
- mADA subject classification (for subset of subjects)
- Overall subject classification (based on ADA and mADA analysis)
- NAb subject classification (all subjects)
- NECA subject classification (all subjects)

2.4.5.5.2 ADA and mADA analysis

ADA

Immunogenicity samples will be evaluated in a three-tiered homogenous bridging ADA assay (screen/confirmatory/titer tiers). All samples confirmed positive in the ADA assay will be titrated. The log₁₀ (titer) will be reported. The titer represents the last dilution factor of the sample's titration series still scoring positive in the ADA assay.

Samples scoring negative in the ADA assay are not titrated and the respective log₁₀ (titer) is reported as < log₁₀ (Minimal required dilution [MRD]) with MRD = 96, i.e. log₁₀ (titer) < 1.98. The latter are not included in descriptive statistics on titers.

Subjects will be classified as follows based on the ADA assay results:

1. ADA negative: no positive ADA samples at any of the sampling time points
2. ADA positive: positive ADA samples at one or more sampling time points
3. Inconclusive: no positive ADA samples and drug is present at levels higher than the drug tolerance characteristics of the assay. Drug tolerance limit is 10µg/mL.
4. Missing: missing will only be used if samples were taken but no reportable result could be obtained for that subject.

Based on these ADA results, no statement can be made on pre-existing antibody (pre-Ab) positivity pre-dose due the plasma exchange (PE) procedure. During PE (i) pre-Ab present in donor plasma can be transferred to the subject and/or (ii) pre-Ab might be diluted during PE treatment. PE is part of the standard of care and no ADA pre-PE sample will be available to determine the pre-Ab status of the subject.

mADA

All confirmed positive ADA samples will be further evaluated in a mADA assay. This assay employs a modified caplacizumab molecule as detection reagent in the bridging format, ie, caplacizumab-Ala variant. The modification constitutes of a single alanine extension at the C-terminus of caplacizumab. The mADA assay allows detection of drug-induced treatment-emergent (TE) ADA, whereas pre-Ab is not detected. In other words, drug-induced TE ADA will score positive in the mADA assay. All samples confirmed positive in the mADA assay will be titrated and reported as log₁₀ (titer). Samples scoring negative in the mADA assay are not titrated and the respective log₁₀ (titer) is reported as < log₁₀ ([MRD) with MRD = 96, ie, log₁₀ (titer) < 1.98. The latter are not included in descriptive statistics on titers.

Subjects will be classified as follows based on the mADA assay results:

1. Pre-Ab positive - Drug-induced TE ADA negative: all ADA positive samples analyzed in the mADA assay score negative ⁽ⁱ⁾
2. Pre-Ab negative - Drug-induced TE ADA positive: all ADA positive samples analyzed in the mADA assay score positive ⁽ⁱⁱ⁾
3. Pre-Ab positive - Drug-induced TE ADA positive: from the ADA positive samples analyzed in the mADA assay, some score positive and some score negative ⁽ⁱⁱ⁾
4. Inconclusive: no positive ADA samples in the mADA assay and drug is present at levels higher than the drug tolerance characteristics of the assay. Drug tolerance limit is 10 µg/mL.
5. Missing: Relevant samples are missing.

(i) Pre-Ab can originate from the donor plasma introduced during PE procedure or can originate from the subject itself.

(ii) Subjects will be classified “pre-Ab negative- drug-induced TE ADA positive”, in case all ADA positive samples analyzed in the mADA assay are positive in the latter assay.

Overall subject classification

For the overall subject classification, subjects will be classified as follows based on the ADA and /or mADA assay results:

1. Pre-Ab negative - Drug-induced TE ADA negative: no positive ADA samples
2. Pre-Ab positive - Drug-induced TE ADA negative: all ADA positive samples analyzed in the mADA assay score negative

3. Pre-Ab negative - Drug-induced TE ADA positive: all ADA positive samples analyzed in the mADA assay are positive
4. Pre-Ab positive - Drug-induced TE ADA positive: from the ADA positive samples analyzed in the mADA assay, some are positive and some are negative
5. Inconclusive: no positive ADA samples or positive mADA samples and drug is present at levels higher than the drug tolerance characteristics of the assay. Drug tolerance limit is $10\mu\text{g/mL}$.
6. Missing: Relevant samples are missing.

Subjects classified “ADA negative” based on ADA assay results will per default be classified as “Pre-Ab negative- Drug-induced TE ADA negative” for the overall subject classification (#1). No results will be reported for samples not evaluated in the mADA assay (#6).

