Physical examination	X	X	X	X	X	X	X
Body weight	X	X	X	X	X	X	X
Height	X						
SF-36	X	X	X	X	X	X	X
RBANS ^d	X						X
HIT-6 TM	X	X	X	X	X	X	X
Clinical laboratory analyses + urinalysis ^e	X	X	X	X	X	X	X
Organ damage markers: TnI	X	X	X	X	X	X	X
ADAMTS13 activity	X	X	X	X	X	X	X
PD parameter : vWF:Ag	X	X	X	X	X	X	X
Immunogenicity (ADA panel)	X	X	X	X	X	X	X

^a The Screening/Baseline Visit will coincide with or is to be scheduled to take place within 1 month after the Final (28 day) FU visit in the preceding Study ALX0681-C301 (HERCULES). Note: for subjects for whom the Final (28 day) FU visit occurred prior to local approval and site activation for this study, a time window of + 1 month after site activation is permitted to complete the screening/baseline visit.

^b Medical history, including general and TTP-related medical history (TTP episodes and major thromboembolic events, e.g., myocardial infarction, cerebrovascular accident, pulmonary embolism, deep venous thrombosis, transient ischemic attack, heart failure, unstable angina, coronary revascularization), and history of hypersensitivity to IMP in Study ALX0681-C301.

^c Heart rate and blood pressure to be assessed after 5 min in supine position.

^d Only in those countries where RBANS is available in the local language(s).

^e Clinical laboratory analyses include hematology (Hb, Hct, RBC, WBC, platelets); chemistry (AST, ALT, LDH, creatinine, protein, cholesterol and CRP). Urinalysis includes assessment of albumin.

Table 2: Schedule of assessments in case of TTP recurrence **

Study Period	Recurrence Period				Recurrence FU visit 7 (±1) days after end of treatment with caplacizumab
	Recurrence Visit	Caplacizumab Treatment Period			
Study Visit		Day 3 visit Caplacizumab Treatment Day 3	Week 1 visit Post-daily PE Day 1 (1 day after last daily PE)	Weekly visits till end of treatment with caplacizumab Post-daily PE Day 8, 15, 22, 29, ... (±1 day)	
Review of caplacizumab treatment criteria	X				
Pregnancy test ^a	X				
TTP recurrence information ^b	X		X		X
Study drug administration					
PE information			X		
Concomitant medication					>
Adverse events					>
Supine heart rate & blood pressure ^c	X	X	X	X ^d	X
Physical examination	X	X	X	X ^d	X
SF-36					X
Clinical laboratory analyses + urinalysis ^e	X	X	X	X	X
Organ damage markers: TnI ^f	X	X	X	X	X
ADAMTS13 activity ^f	X	X	X	X	X
Immunogenicity (ADA panel) ^{f,g}	X	X	X	X	X
PK ^f	X	X	X	X	X
PD parameters ^{f,h}	X	X	X	X	X

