1.2.5. SAFETY PROFILE AND RISK ASSESSMENT

The benefit and risk assessment for administration of caplacizumab, as detailed in the Investigator's Brochure, supports initiation of the proposed clinical study.

Overall, Study ALX-0681-2.1/10 (TITAN study) provided evidence for the clinical efficacy of caplacizumab as potential treatment for patients with acquired TTP who were receiving standard of care therapy, with respect to reducing the time-to-response (based on confirmed recovery in platelet counts) and reducing the incidence of exacerbation during treatment. These findings were associated with tangible clinical benefits in terms of reduced mortality/morbidity [17]. The higher incidence of relapse soon after discontinuation of caplacizumab appeared to be associated with persistent low ADAMTS13 activity (<10%), suggesting unresolved underlying auto-immune activity. Study ALX0681-C301 and this study will evaluate whether such patients would benefit from continuing treatment with caplacizumab for a longer period after discontinuation of PE.

The safety results in the TITAN study revealed no unexpected findings in relation to AEs. The main safety finding associated with caplacizumab treatment was an increase in bleeding-related AEs, which was consistent with findings in previous studies and is an expected consequence of the pharmacological activity of the drug. Notwithstanding this, the majority of bleeding events in the study were mild to moderate in severity, and an equal number of subjects in each treatment arm (2 subjects per arm) had a serious bleeding related TEAE. Hence, bleeding risk appears to be acceptable in the context of the clinical benefits of caplacizumab in the TTP indication. Nonetheless, vWF preparations can be used as antidote to caplacizumab if needed. vWF and FVIII preparations as combination products are commercially available.

With regard to immunogenicity, taking into account patient, product and disease related factors, caplacizumab was assigned a low risk class designation. In the TITAN study, drug induced TE antibodies were detected in 9% of caplacizumab treated subjects. No immunogenicity related safety findings were reported. Whether retreatment with caplacizumab includes a risk for inducing ADA is currently unknown.

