3.4.11. APPROPRIATENESS AND TIMING OF MEASUREMENTS

The assessments which will be made in this study are standard and generally recognized as reliable, accurate, and relevant.

The timing of all assessments is detailed in the [Schedules of Assessments](#).

Note that blood samples for ADA, PD parameters and disease-related markers need to be collected prior to start of the PE treatment and/or study drug administration (whatever comes first; at the recurrence visit and the Treatment Day 3 visit) or prior to study drug administration (at all subsequent recurrence visits).

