9. APPENDIX

Appendix 1: Schedule of Assessments in Case of TTP Recurrence (in Case Treatment With Caplacizumab is not Initiated)

Study Period	Recurrence Period (no caplacizumab)	
	Recurrence Visit Recurrence Day 1	Recurrence FU visit 30 days after end of daily PE
TTP recurrence information ^a	X	X
PE information		X
Concomitant medication		→
Adverse events		→
Supine heart rate & blood pressure ^b	X	X
Physical examination	X	X
SF-36		X
Clinical laboratory analyses + urinalysis ^c	X	X
Organ damage markers: TnI ^d	X	X
ADAMTS13 activity ^d	X	X
Immunogenicity (ADA panel) ^d	X	
PD parameter : vWF:Ag ^d	X	X

^a TTP recurrence information includes presenting symptoms (assessed at recurrence visit), duration and outcome (assessed at the recurrence FU visit).

^b Heart rate and blood pressure to be assessed after 5 min in supine position.

[figure not shown]
^c Clinical laboratory analyses include hematology (Hb, Hct, RBC, WBC, platelets); chemistry (AST, ALT, LDH, creatinine, protein, cholesterol and CRP). Urinalysis includes assessment of albumin. The results of assessment of platelet count and LDH levels performed as per standard of care (by a local laboratory) at any time during the recurrence period will be collected in the eCRF, if available.

^d Samples need to be collected prior to start of the first PE treatment.

Signature Page

This is a representation of an electronic record that was signed electronically in Livelink.
This page is the manifestation of the electronic signature(s) used in compliance with the organizations
electronic signature policies and procedures.

Date: [Redacted]

Meaning: Approved

=====

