Study Visit	Recurrence Visit	Day 3 visit Treatment Day 3	Week 1 visit Post-daily PE Day 1 (1 day after last daily PE)		
Review of caplacizumab treatment criteria	X				
Pregnancy test ^a	X				
TTP recurrence information ^b	X		X		X
Study drug administration				>	
PE information			X		
Concomitant medication					>
Adverse events					>
Supine heart rate & blood pressure ^c	X	X	X	X ^d	X
Physical examination	X	X	X	X ^d	X
SF-36					X
Clinical laboratory analyses + urinalysis ^e	X	X	X	X	X
Organ damage markers: TnI ^f	X	X	X	X	X
ADAMTS13 activity ^f	X	X	X	X	X
Immunogenicity (ADA panel) ^{f,g}	X	X	X	X	X
PK ^f	X	X	X	X	X
PD parameters ^{f,h}	X	X	X	X	X

^a Pregnancy test (urine or blood) for female subjects of childbearing potential will be assessed per local laboratory.

^b TTP recurrence information includes presenting symptoms (assessed at recurrence visit), duration (assessed at the Week 1 visit) and outcome (assessed at the recurrence FU visit).

^c Heart rate and blood pressure to be assessed after 5 min in supine position.

^d To be assessed at the post-daily PE Day 29 only.

^e Clinical laboratory analyses include hematology (Hb, Hct, RBC, WBC, platelets); chemistry (AST, ALT, LDH, creatinine, protein, cholesterol and CRP). Urinalysis includes assessment of albumin. The results of assessment of platelet count and LDH levels performed as per standard of care (by a local laboratory) at any time during the recurrence period will be collected in the eCRF, if available.

- f* At the recurrence visit and the Treatment Day 3 visit, samples need to be collected prior to start of the PE treatment and/or study drug administration (whatever comes first). At all subsequent visits, blood samples need to be taken prior to study drug administration.
- g* In case of a severe and/or serious hypersensitivity reaction, an additional blood sample to characterize the reaction should be collected as soon as possible after the start of the event.
- h* PD parameters include RICO and vWF:Ag.

Table 6 Schedule of Assessments in Case of TTP Recurrence (in Case Treatment with Caplacizumab is not Initiated)

Study Period	Recurrence Period (no caplacizumab)	
	Recurrence Visit Recurrence Day 1	Recurrence FU visit 30 days after end of daily PE
TTP recurrence information ^a	X	X
PE information		X
Concomitant medication		→
Adverse events		→
Supine heart rate & blood pressure ^b	X	X
Physical examination	X	X
SF-36		X
Clinical laboratory analyses + urinalysis ^c	X	X
Organ damage markers: TnI ^d	X	X

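### The SAP denies a pre-PE ADA sample that both schedules plan, and its mADA classes ignore timing, so antibody carried over from C301 and antibody arising on C302 retreatment share one class

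*SAP*

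**What the plan says.** **Premise.** SAP 2.4.5.5.2 declines to judge pre-existing antibody (pre-Ab) before dosing, because donor plasma may add it and PE may dilute it. It adds that "no ADA pre-PE sample will be available to determine the pre-Ab status of the subject".

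**Sampling.** Footnote f of Table 5 in SAP Appendix A is attached to the ADA row. For the recurrence visit and Treatment Day 3 it says "samples need to be collected prior to start of the PE treatment and/or study drug administration (whatever comes first". Protocol Table 2 has the same footnote, and Protocol 3.4.11 names ADA: "blood samples for ADA, PD parameters and disease-related markers need to be collected prior to start of the PE treatment and/or study drug administration". For recurrences without caplacizumab, Protocol Appendix 1 (repeated in SAP Table 6) says "Samples need to be collected prior to start of the first PE treatment". Protocol Table 1 and SAP Table 4 add ADA samples at screening/baseline and at all six follow-up visits.

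**Classification.** SAP 2.4.5.5.2 relies on assay specificity: "drug-induced TE ADA will score positive in the mADA assay". A subject is pre-Ab negative and drug-induced TE ADA positive when "all ADA positive samples analyzed in the mADA assay score positive". Mixed mADA results make the subject positive for both. If all are negative, the subject is pre-Ab positive only.

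**Aim.** Protocol 1.2.5 says: "Whether retreatment with caplacizumab includes a risk for inducing ADA is currently unknown". The synopsis lists immunogenicity of (repeated) treatment among the main endpoints. Protocol 3.6.5 undertakes to assess the effect of retreatment on immunogenicity and refers to C301 ADA results when defining pre-Ab and TE status.

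**The concern.** The availability clause contradicts the sampling schedule in the SAP's own appendix.

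Separately, the mADA assay distinguishes drug-induced antibody from pre-Ab, but it cannot show which course of drug induced it. In a follow-up study where many subjects were already exposed in C301, a class without a pre-dose reference puts three situations together: antibody left over from C301, antibody newly induced by C302 retreatment, and older antibody boosted by it. The open question in Protocol 1.2.5 concerns the last two.

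The classes are also used beyond the summary counts. SAP 2.4.5.5.5 uses them to group drug concentration, vWF:Ag, RICO, time to platelet response and hypersensitivity.

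**Working it through.** **Step 1: is a reference sample planned?** Yes. There are seven scheduled time points outside recurrence periods (baseline plus six visits), and one sample per recurrence visit due before PE and/or drug. SAP 2.4.5.5.3 itself analyses the baseline visit and recurrence visit day 1 for NAb. SAP 2.1.1 and 2.4.5 define the recurrence visit as baseline for recurrence-period analyses.

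**Step 2: do the classes use it?** No. The mADA and overall classes depend only on whether all, some or none of a subject's ADA-positive samples are mADA-positive. They carry no visit, dose or titre condition, so reordering a subject's samples never changes the class.

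**Step 3: apply the rules.** The comparator is a rule of the kind the SAP uses for NECA (2.4.5.5.4), with the last pre-dose sample as reference, or C302 baseline if the subject is never dosed. TE positive then means newly positive, or a log10 titre rise above log10(1.89) = 0.276. The value 1.89 is the NECA MSR and is borrowed here only to show the logic.

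| Pattern in C302 | SAP mADA/overall class | Anchored rule |
|---|---|---|
| A. mADA-positive at baseline only, never dosed | pre-Ab negative, TE positive | pre-dose positive, TE negative |
| B. Stable positive throughout, never dosed | same | pre-dose positive, TE negative |
| C. Retreated, positive only in the pre-PE recurrence sample | same | pre-dose positive, TE negative |
| D. Retreated, same titre before and after | same | pre-dose positive, TE negative |
| E. Retreated, negative before, positive after | same | pre-dose negative, TE positive |

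A two-fold boost (log10 2 = 0.301 > 0.276) would be pre-dose positive, TE positive under the anchored rule.

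There is also a tension with SAP 2.1.4, which does not call adverse events treatment-emergent in a recurrence where no drug was given. Under 2.4.5.5.5, a subject in the not-treated recurrence group who carries C301 antibody can still be tabulated as drug-induced TE positive.

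**Step 4: illustrative size.** The plan states no figure to reproduce. Inputs:
- N = 92/2 = 46, the planned C301 caplacizumab arm (Protocol 1.2.4), assuming all enrol.
- r = 9%, the TE ADA rate in the Phase II TTP study (Protocol 1.2.4).
- s = the share of antibody persisting to C302 baseline, an assumption.

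Expected carry-over = N × r × s, and P(at least 1) = 1 − (1 − r × s)^46:
- s = 25%: 46 × 0.09 × 0.25 = 1.0; P = 0.65
- s = 50%: 46 × 0.09 × 0.50 = 2.1; P = 0.88
- s = 100%: 46 × 0.09 × 1.00 = 4.1; P = 0.99

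With r from 3% to 15%, the range is 46 × 0.03 × 0.25 = 0.3 to 46 × 0.15 × 1.00 = 6.9.

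If 10 to 20 subjects are retreated (an assumption) and the same 9% applies, new inductions are 10 × 0.09 = 0.9 to 20 × 0.09 = 1.8. The ratio of carry-over to new induction then runs from 1.035/1.8 = 0.6 to 4.14/0.9 = 4.6.

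**The case against.** **Pre-PE may mean before any PE at all.** Protocol 1.2.4 says C301 subjects were randomized after PE had started, so no C302 sample precedes all PE. The donor-plasma and dilution caveat is therefore legitimate and should stay. It concerns pre-existing antibody, however. The C302 baseline and recurrence-visit samples can still serve as the reference for emergence in C302.

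**The label is not false for C301.** A never-retreated subject who is mADA-positive at C302 baseline does have drug-induced antibody, and the ITO immunogenicity groups are defined by C301 exposure. The parentheses around repeated in the endpoint also show that it is not confined to retreatment. This stands. The error lies in reading that class as emergence in C302.

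**The timing is not lost.** SAP 2.4.5.5.5 plans by-visit mADA incidence, titre-time plots and listings at every time point, and NECA has its own baseline-anchored class. This also stands. The limitation is confined to the subject-level mADA and overall classes and to analyses built on them.

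**A clean reference does not exist for every episode.** When daily PE is restarted during an ongoing recurrence period, the new recurrence-visit sample can follow recent PE and caplacizumab. A reader might infer that each treated episode has an unexposed sample, but the documents do not support that. The fix has to handle this case.

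**Conclusion.** The point holds. The availability clause conflicts with the SAP's own Appendix A and with the protocol. The mADA and overall classes cannot separate carry-over from induction or boosting by C302 retreatment. NAb and NECA, by contrast, are referenced to the baseline visit. In a descriptive study this should be corrected, but it is not a fundamental flaw.

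Three stronger readings are not supported:
- That the rules ignore timing because of the mistaken clause. The SAP does not say so, and the stated basis for the mADA class is assay specificity.
- That the C302 TE ADA rate is inflated as a matter of fact. The documents give no persistence data.
- That carry-over will outnumber new induction several-fold. At full enrolment and full persistence the illustration gives 4.1 against 0.9 to 1.8, but at 25% persistence the two are of similar size.

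The illustration of about 1 to 4 carry-over subjects against about 1 to 2 new inductions rests on assumed enrolment, persistence and retreatment numbers. It also leaves out C301 placebo subjects who crossed over to open-label caplacizumab, for whom the documents give no count.

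**What to change.** 1. In SAP 2.4.5.5.2, correct only the last clause on sample availability and keep the donor-plasma and dilution caveat.
2. For retreated subjects, add a class anchored to the last sample before the first C302 dose. This is the recurrence-visit sample or, if that is missing, the last six-monthly or C302 baseline sample. The categories are: negative throughout; mADA-positive before dose without a rise; newly mADA-positive after dose; boosted.
3. Define boosted by the validated MSR of the ADA/mADA assay. The sponsor must supply it, because 1.89 is stated for NECA only.
4. For a recurrence within an ongoing recurrence period, keep the reference from before the first dose of that treatment sequence.
5. In the ITO summary, report mADA-positive at C302 baseline (attributable to C301) separately from mADA-positive first arising after a C302 dose.

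The cost is SAP wording and some extra derivation. No new samples are needed, and mADA-positive samples are already titrated. The downside is small cell counts, so the new classes are best shown as counts alongside the planned listings.

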(1) caplacizumab-treated, defined as subjects in the ITO population who have been randomized to caplacizumab in Study ALX0681-C301, evaluated up to their first recurrence⁺⁺⁺; (2) standard of care-treated, defined as subjects in the ITO population who have been randomized to placebo in Study ALX0681-C301, evaluated up to their first recurrence.

All efficacy endpoints related to assessments during the recurrence period will be analyzed using the recurrence population. The effect of retreatment of caplacizumab on these endpoints will be evaluated.

Select sensitivity analyses may be planned to assess the effect of heterogeneity in the timings of the baseline visit between subjects. More details will be provided in the SAP. Unless specified otherwise, no missing data imputation will be applied, and all efficacy endpoints will be analyzed as observed.

3.6.5. EVALUATION OF PHARMACOKINETIC AND PHARMACODYNAMIC, DISEASE RELATED MARKERS AND IMMUNOGENICITY PARAMETERS

Individual study drug concentrations will be listed. In addition a listing of the actual sampling times relative to the study drug administration times will be presented.

Drug concentrations will be summarized by sampling time using descriptive statistics and will be listed and summarized in tabular and/or graphical form.

All PD and disease-related marker data will be summarized using descriptive statistics and will be listed and summarized in tabular and/or graphical form.

Immunogenicity will be assessed through listing of individual (ADA, mADA and nAb) results by subject, summary tables and immunogenicity time profiles. Immunogenicity data will be correlated with PK and PD readout using descriptive statistics per subject category based on pre-Ab and TE ADA status (using ADA results obtained in Study ALX0681-C301), summarized in tabular and/or graphical form. In addition, immunogenicity will be correlated with possible safety findings. The effect of retreatment with caplacizumab on immunogenicity will be assessed.

⁺⁺⁺ Subjects who had a recurrence during Study ALX0681-C301 or between the Final (28 day) FU visit in Study ALX0681-C301 and Screening/Baseline in Study ALX0681-C302, will not be considered for the group-wise analyses.

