2.4.5.5.5 Analysis

Immunogenicity will be assessed through summary tables, figures, and listing of individual results by subject. All immunogenicity data related to assessments on the Q6M FU visits will be analyzed using the ITO population on the following analysis groups:

- Caplacizumab total: Subjects who received caplacizumab during the ALX0681-C301 study (during the double blind or the open-label periods).
- Not treated: Subjects who never received Caplacizumab during the ALX0681-C301 trial

All immunogenicity data related to assessments during the recurrence periods will be analyzed using the recurrence population with the following analysis groups:

- Treated with IMP: patients treated with caplacizumab in the ALX0681-C302 study for the specific recurrence episode
- Not Treated with IMP: patients not treated with caplacizumab in the ALX0681-C302 study for a specific recurrence episode

ADA assay results

The number and percentage of subjects per ADA subject category will be summarized.

Incidence of positive ADA samples by visit.

Spaghetti plot of ADA log₁₀ (titer) vs. time. Negative values for ADA (reported as log₁₀ (titer) < 1.98) will be visualized on the graphs as 1.80 (arbitrarily chosen) to allow plotting. The MRD (or sensitivity of the assay) will be visualized as horizontal line at log₁₀ (titer) = 1.98.

mADA assay results

The number and percentage of subjects per mADA subject category will be summarized. This tabulation and analysis will be performed on a subset of the population, consisting of subjects who were classified as ADA positive based on ADA data.

- Each mADA subject category
- Classified as TE ADA within the pre-Ab negative and within the pre-Ab positive population
- Classified as pre-Ab negative, pre-Ab positive, drug-induced TE negative and drug-induced TE positive

Incidence of positive mADA samples by visit.

Spaghetti plot of mADA log₁₀ (titer) vs. time. Negative values for mADA (reported as log₁₀ (titer) < 1.98) will be visualized on the graphs as 1.80 (arbitrarily chosen) to allow plotting. The MRD (or sensitivity of the assay) will be visualized as horizontal line at log₁₀ (titer) = 1.98.

ADA/mADA assay results (overall subject classification)

The number and percentage of subjects will be summarized by group using following categorization.

- Each overall subject category
- Classified as TE ADA within the pre-Ab negative and within the pre-Ab positive population

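### The SAP labels a subject pre-Ab negative when every ADA-positive sample is also mADA positive, a pattern that cannot exclude pre-existing antibody, so the TE ADA rates by pre-Ab stratum can be distorted

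*SAP*

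**What the plan says.** SAP 2.4.5.5.2 describes two assays. The bridging ADA assay is run on all immunogenicity samples. For the second, "All confirmed positive ADA samples will be further evaluated in a mADA assay", and "The mADA assay allows detection of drug-induced treatment-emergent (TE) ADA, whereas pre-Ab is not detected".

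Subjects are then labelled from the pattern of results. Category 2 of the mADA classification is "Pre-Ab negative - Drug-induced TE ADA positive: all ADA positive samples analyzed in the mADA assay score positive"; category 3 of the overall classification uses the same rule. A subject is pre-Ab positive and TE ADA positive only if, "from the ADA positive samples analyzed in the mADA assay, some are positive and some are negative". The overall classification also has "Pre-Ab negative - Drug-induced TE ADA negative: no positive ADA samples", which the mADA classification lacks.

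SAP 2.4.5.5.5 tabulates subjects "Classified as TE ADA within the pre-Ab negative and within the pre-Ab positive population", for both the mADA and the overall classification. The mADA table is restricted to a subset "consisting of subjects who were classified as ADA positive based on ADA data". The same section plots drug concentration, vWF:Ag, RICO and time to platelet response by subject category, and splits a hypersensitivity analysis by the overall classification.

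Protocol 3.6.5 plans to relate immunogenicity to PK and PD by subject category "based on pre-Ab and TE ADA status (using ADA results obtained in Study ALX0681-C301"). The SAP's classification rules do not mention C301 results.

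**The concern.** Only an ADA-positive, mADA-negative sample is evidence of pre-Ab. The lack of such a sample is not evidence that pre-Ab is absent, because drug-induced antibody in the same sample hides it. The rule nevertheless turns that lack into a definite negative.

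Masking is plausible in this study. Subjects who received caplacizumab in C301 may already carry drug-induced antibody at the C302 baseline. If it persists, no C302 sample can show pre-Ab on its own.

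The outputs at stake are the TE ADA rates within the pre-Ab strata, the apparent pre-Ab prevalence, the plots by category and the hypersensitivity subgroup analysis. Immunogenicity of (repeated) treatment is one of the main endpoints in the protocol synopsis, so these tables will be read.

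**Working it through.** The plan states no figure for this classification, so there is none to reproduce. The check has four steps.

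**1. Which true states are mislabelled?** Assume error-free assays: ADA is positive if pre-Ab or TE ADA is present, and mADA is positive if TE ADA is present. Each sample has four possible states, so three samples give 4³ = 64 profiles.

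- Neither type at any time: 1 profile, labelled correctly.
- TE ADA only: 2³ − 1 = 7, labelled correctly.
- Pre-Ab only: 7, labelled correctly.
- Both types at some time: 64 − 1 − 7 − 7 = 49. The profiles with no pre-Ab-only sample but at least one doubly positive sample number 3³ − 2³ = 27 − 8 = 19. These 19 are labelled pre-Ab negative; the other 30 are labelled correctly.

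These are counts of patterns, not probabilities. They show that under error-free assays the only error is from pre-Ab positive/TE positive to pre-Ab negative/TE positive.

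**2. Effect on the overall-classification rates.** Let π be the true pre-Ab prevalence, t the true TE ADA rate (taken as equal in both strata), and q the share of doubly positive subjects with no ADA-positive, mADA-negative sample.

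- Reported pre-Ab negative rate = [(1 − π)t + πtq] / [(1 − π) + πtq]
- Reported pre-Ab positive rate = t(1 − q) / (1 − tq)

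The values of π and q are assumptions. For t, Protocol 1.2.4 reports 9% in the Phase II TTP study and 10.9% in the Phase II coronary intervention study.

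Illustration with 100 subjects, π = 40%, t = 10%. The true cells are 54 (neither), 6 (TE ADA only), 36 (pre-Ab only) and 4 (both).

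| q | Subjects moved | Pre-Ab negative rate | Pre-Ab positive rate |
|---|---|---|---|
| 0 | 0 | 6/60 = 10% | 4/40 = 10% |
| 25% | 1 | 7/61 = 11.5% | 3/39 = 7.7% |
| 50% | 2 | 8/62 = 12.9% | 2/38 = 5.3% |
| 100% | 4 | 10/64 = 15.6% | 0/36 = 0% |

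With t = 9% and π = 30%, the rates are 9.9% versus 6.9% at q = 25%, 10.7% versus 4.7% at q = 50%, and 12.4% versus 0% at q = 100%. With t = 9%, q = 50% and π from 10% to 60%, the pre-Ab negative rate runs from 9.5% to 14.8%, and the pre-Ab positive rate is 4.7% throughout. The pooled TE ADA rate equals t in every case.

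**3. What the data can support.** Let n1 to n4 be the counts in overall categories 1 to 4. If the pre-Ab status of the n3 subjects is unknown:

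- the pre-Ab negative rate lies between 0 and n3/(n1 + n3);
- the pre-Ab positive rate lies between n4/(n2 + n4) and (n3 + n4)/(n2 + n3 + n4).

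In the 25% row, n1 = 54, n2 = 36, n3 = 7 and n4 = 3. The bounds are 0 to 11.5%, and 3/39 = 7.7% to 10/46 = 21.7%. Both contain the true 10%. Dropping the n3 subjects would instead give 0/54 = 0% and 3/39 = 7.7%, which are both too low.

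**4. The mADA-only table.** Its denominator is ADA-positive subjects and it has no category negative for both types. Every subject labelled pre-Ab negative is therefore TE positive, and that stratum's rate is 100% whatever the data. This would remain with perfect labels, so it is a separate defect.

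**The case against.** The strongest case against is that the effect may be small or absent. A reader might infer that a single positive mADA result makes a subject pre-Ab negative, or that bias is certain by construction. The SAP does not say the first: all ADA-positive samples must be mADA positive, and any mixed pattern gives pre-Ab positive. Seven scheduled ADA visits, plus recurrence samples, offer several chances to catch one revealing sample. If every doubly positive subject has one, the bias is zero. This limits the size of the problem, but nothing in the documents ensures it.

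The direction is not guaranteed either. If the mADA assay misses low-titer drug-induced antibody, that sample counts as evidence of pre-Ab and the error runs the opposite way. The documents give no mADA sensitivity.

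The numbers involved are small. C301 planned about 92 subjects randomized 1:1, so roughly 46 to caplacizumab. Under the illustrative assumptions that is 46 × 0.4 × 0.1 = 1.84, or about 2 doubly positive subjects, before allowing for non-participation on one side and for crossover and retreatment on the other.

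It is tempting to say that C301 results simply solve the problem, or that Protocol 3.6.5 prescribes pre-exposure C301 samples. Neither is supported. The protocol sentence does not mention pre-exposure samples. Protocol 1.2.4 says C301 subjects were randomized after PE had started, and SAP 2.4.5.5.2 warns that PE can transfer donor pre-Ab or dilute the subject's own. C301 pre-dose samples may carry that same limitation.

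These points reduce the size and change the remedy. They do not rescue the inference from an all-mADA-positive pattern to pre-Ab negative. The SAP's own PE caveat makes a definite label harder to defend.

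**Conclusion.** The concern holds as a labelling defect with consequences for stratified descriptive results. The SAP's account of the assay does not support the pre-Ab negative label in mADA category 2 and overall category 3. Under error-free assays the reported TE ADA rate is too high in the pre-Ab negative stratum and too low in the pre-Ab positive stratum whenever some doubly positive subjects are masked. The size cannot be determined from the documents; in the 100-subject illustration 1 to 4 subjects move.

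A reader might go on to infer that the immunogenicity endpoint as a whole is unreliable, or that the trial will conclude that pre-Ab protects against drug-induced ADA. The documents do not support this. Pooled TE ADA incidence, ADA and mADA incidence by visit, titers, and the NAb and alternative NAb results do not depend on this label. SAP 2.4.4.8 plans no formal test, and the SAP plans no statement on protection. The change should be made, but the main immunogenicity result does not depend on it.

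**What to change.** 1. In both the mADA and the overall classification, rename the category *pre-Ab undetermined, drug-induced TE ADA positive*.
2. Report pooled TE ADA incidence, (n3 + n4)/(n1 + n2 + n3 + n4), as the main result.
3. In the overall table, replace the TE ADA percentages within pre-Ab strata by the bounds given above, or drop them. Do not simply exclude the undetermined subjects.
4. Remove the within-stratum rate from the mADA-only table.
5. Carry the new label into the plots by category and the hypersensitivity subgroup analysis.
6. Use C301 ADA results to resolve pre-Ab status only where a pre-exposure sample exists and can be interpreted given prior PE.
7. Reconcile the SAP 2.4.5.5.2 statement that no pre-PE ADA sample will be available with footnote f of Protocol Table 2 and SAP Table 5, which require the recurrence-visit ADA sample before PE and/or study drug.

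The cost is SAP wording, revised table shells and, where C301 results are usable, a merge of those data. The downside is that some subjects will have undetermined pre-Ab status and the stratum rates become ranges.
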